8.5 Assessment of Relationship to Study Drug (Causality)

Investigators are required to assess the causal relationship (i.e., whether there is reasonable possibility that the study drug caused the event) using the following definitions:

Unrelated: Another cause of the adverse event is more plausible; a temporal sequence cannot be established with the onset of the adverse event and administration of the investigational product; or, a causal relationship is considered biologically implausible.

Possibly Related: There is clinically plausible time sequence between onset of the adverse event and administration of the investigational product, but the adverse event could also be attributed to concurrent or underlying disease, or the use of other drugs or procedures. Possibly related should be used when the investigational product is one of several biologically plausible adverse event causes.

Definitely Related: The adverse event is clearly related to use of the investigational product.

8.6 Severity of Adverse Events (Grading)

Adverse events will be categorized and graded by the Investigator using standard terminology for grading the severity (intensity) of the AE. This study will use the NCI Common Terminology Criteria for Adverse Events (NCI CTCAE v 4.0) five-point scale, Grades 1 to 5 with unique clinical descriptions of severity for each referenced AE. A copy of the CTCAE version 4.0 can be downloaded from the CTEP website at: http://ctep.cancer.gov/protocolDevelopment/electronic_applications/ctc.htm. A hard copy will be provided by BNI upon request.

Should a subject experience any AE not listed in the CTCAE v4.0, the following grading system should be used to assess severity:

Table 9-1 Adverse Event Grading Criteria

CTCAE Grade	Equivalent To:	Definition
Grade 1	Mild AE	Experiences which are usually transient, requiring no special treatment, and no disruption of normal daily activity
Grade 2	Moderate AE	Experiences which introduce some level of inconvenience or concern to the subject, and which may interfere with daily activities, but are usually ameliorated by simple therapeutic measures

Grade 3	Severe AE	Experiences which are unacceptable or intolerable, significantly interrupt the subject's usually daily activity, and require systemic drug therapy or other treatment
Grade 4	Life threatening / disabling AE	Experience which causes the subject to be in imminent danger of death
Grade 5	Death related to AE	Experiences resulting in subject death

8.7 Dose Modifications for Toxicity

There are no dose reductions or modifications for dose toxicity for PROSTVAC-V/F. If subjects experience intolerable toxicities due to PROSTVAC-V/F, they will be removed from treatment and will be immediately rolled over onto the Long-Term Follow-Up (LTFU) phase of the study and followed for safety and vital status per protocol.

8.8 Definition of Serious Adverse Events

Note: The terms "severe" and "serious" are not synonymous. Severity (or intensity) refers to the grade of an AE (see below). "Serious" is a regulatory definition. A serious adverse event (experience) or reaction is an untoward medical occurrence that at any dose:

- Results in death (i.e., the AE actually causes or leads to death)
- Is life-threatening (with regards to determining if an AE is serious, "life-threatening" is defined as an AE in which the subject was at risk of death at the time of the event. It does not refer to an event which hypothetically might have caused death if it were more severe. If either the Investigator or the Sponsor believes that an AE meets the definition of life-threatening, it will be considered life-threatening).
- Requires in-patient hospitalization or prolongation of existing hospitalization
- Results in persistent or significant disability/incapacity (i.e., the AE results in substantial disruption of the subject's ability to conduct normal life functions)
- Results in a congenital anomaly/birth defect
- Is medically significant

Medical and scientific judgment should be exercised in deciding whether other situations, such as important medical events that may not be immediately life-threatening or result in death or hospitalization but may jeopardize the subject or may require intervention to prevent one of the other outcomes listed in the definition above, should also be considered serious. Examples of such events are intensive treatment in an emergency room or at home for allergic bronchospasm; blood dyscrasias or convulsions that do not result in hospitalization; or development of drug dependency or drug abuse). Given the Investigator's

perspective may be informed by having actually observed the event, the Sponsor is likely to have broader knowledge of the drug and its effects to inform its evaluation of the significance of the event, if either the Sponsor or the Investigator believes that the event is serious, the event will be considered serious.

For the purposes of this trial, death is an expected outcome of disease progression and/or sequelae and will not be considered an SAE. Death due to causes other than underlying disease progression should be reported on the AE and SAE page and should also be reported on the CRF death page.

For the purposes of this trial, the following will NOT be considered SAEs:

- Hospitalizations < 24 hours, or for planned surgeries or procedures.
- Progression of underlying malignancy as a stand-alone event term; clinical events associated with disease progression should be reported as AEs or SAEs as applicable.
- Death due to progression of underlying malignancy

8.9 Definition of Unexpected Serious Adverse Events

An unexpected SAE is one in which the specificity or severity is not consistent with the current applicable product information (Investigators' Brochure or drug prescribing label), or one that has not been observed previously (rather than from the perspective of such experience not being anticipated from the pharmacological properties of the pharmaceutical product).

8.10 Definition of Suspected Adverse Reaction

The FDA has published guidance on the reporting of SAEs (Safety Reporting requirements for INDs and BA/BE studies, December 2012). This document directs Sponsors to consider more carefully the adverse events that are reported in an expedited (urgent) fashion to the FDA. Key elements of this guidance are outlined below:

The guidance defines any adverse event for which there is a "reasonable possibility" that the drug caused the adverse event as a Suspected Adverse Reaction.

"Reasonable Possibility", for the purposes of safety reporting, means there is evidence to suggest a causal relationship between the drug and the adverse event. Examples of evidence that would suggest a causal relationship between the drug and the adverse event are:

- A single occurrence of an event that is uncommon and known to be strongly associated with drug exposure (e.g., angioedema, blood dyscrasias, rhabdomyolysis, hepatic injury, anaphylaxis, and Stevens-Johnson Syndrome).
- One or more occurrences of an event that is not commonly associated with drug exposure, but is otherwise uncommon in the population exposed to the drug (e.g., include tendon rupture or heart valve lesions in young adults, or intussusception in healthy infants). If the event occurs in association with other factors strongly suggesting causation (e.g., strong temporal association, event recurs on rechallenge), a single case may be sufficiently

persuasive; but often, more than one occurrence (from one or multiple studies) would be needed before the Sponsor could make a determination of whether the drug caused the event.

- An aggregate analysis of specific events that can be anticipated to occur in the study population independent of drug exposure. Such events include known consequences of the underlying disease or condition under investigation (e.g., symptoms or disease progression), or events unlikely to be related to the underlying disease or condition under investigation, but commonly occur in the study population independent of drug therapy (e.g., cardiovascular events in an elderly population). An aggregate analysis (across studies) will identify those events that occur more frequently in the drug treatment group than in a concurrent or historical control group.

This definition of “suspected adverse reaction” and the application of the “reasonable possibility” causality standard is considered to be consistent with the concepts and discussion about causality in the International Conference on Harmonization (ICH) E2A guidance.

8.11 Documenting and Reporting of Adverse Events and Serious Adverse Events

The Investigator is responsible for ensuring that all AEs and SAEs that are observed or reported during the study, as outlined in the prior sections, are recorded on the CRF.

An event may qualify for expedited reporting to worldwide regulatory authorities if it is a Serious Adverse Event, Serious Adverse Drug Reaction or Suspected Unexpected Serious Adverse Reaction (SUSAR) in line with relevant legislation, including the European Commission Clinical Trials Directive (2001/20/EC). Expectedness of SAEs will be determined by BNI using the reference safety information specified in the Investigator’s Brochure. All investigators will receive a safety letter notifying them of relevant SUSAR reports.

In accordance with the European Commission Directive 2001/20/EC, BNIT or designee will notify the relevant Ethics Committees in concerned Member States of applicable SUSARs as individual notifications or through a periodic line listing.

The Sponsor makes the determination of expedited reporting of an SAE to Regulatory Authorities. Regulatory Authorities, Institutional Review Boards/Research Ethics Boards/Independent Ethics Committees (IRBs/REBs/IECs), and Principal Investigators will be notified of SAEs in accordance with applicable requirements (e.g., GCPs, ICH guidelines, national regulations, and local requirements). The Investigator is responsible for complying with the responsible IRB/IEC’s procedures of adverse event reporting. It is the responsibility of the Investigator to promptly inform the relevant IRB/IEC of these new adverse events/risks to subjects, in accordance with the US FDA Code of Federal Regulations (CFR) 21 CFR 312.66.

BNI has an internal medical safety review committee that will review and evaluate accumulating safety data from the entire clinical trial database for PROSTVAC-V/F at appropriate intervals (e.g., quarterly) to identify new safety signals or increased frequency of events.

8.12 Adverse Event Reporting Period

The AE reporting period for this study begins with signing of the informed consent and ends 28 days following administration of the last dose of study medication. If an SAE is present at the EOT Visit, the SAE (and associated AEs and concomitant medications) should be followed to resolution or until the Investigator assesses the subject as stable, or the subject is lost to follow-up or withdraws consent. Resolution/stable means the subject has returned to baseline state of health or the Investigator does not expect any further improvement or worsening of the event.

New SAEs will be collected until 28 days following administration of the last dose of study medication . If an SAE comes to the attention of the investigator after the end of the study, information regarding the SAE should be collected and reported only if assessed as possibly or definitely related by the investigator.

8.13 Assessment of Adverse Events

Investigators will assess the occurrence of AEs and SAEs at all subject evaluation time points during the study. All AEs and SAEs whether volunteered by the subject, discovered by study personnel during questioning, or detected through physical examination, clinically significant laboratory test, or other means will be recorded in the subject's medical record and on the AE CRF and, when applicable, on the Serious Adverse Event (SAE) report form.

[figure not shown]
Each recorded AE or SAE will be described by its duration (i.e., start and end dates), severity, regulatory seriousness criteria (if applicable), suspected relationship to the investigational product, and any actions taken.

Any SAE that occurs after the subject signs informed consent and until 28 days following administration of the last dose of study medication, irrespective of the treatment received by the subject, must be reported to the [REDACTED] PVG within 24 hours of the investigator learning of the event.

8.14 Serious Adverse Events

BNI is required to expedite to worldwide regulatory authorities reports of Serious Adverse Events, Serious Adverse Drug Reactions or Suspected Unexpected Serious Adverse Reactions (SUSARs) in line with relevant legislation, including the European Commission Clinical Trials Directive (2001/20/EC); therefore, BNI (or the CRO on the behalf of BNI) must be notified immediately regarding the occurrence of any SAE or SADR that occurs after the subject consents to participate in the study, including SAEs/SADRs resulting from protocol-associated procedures as defined in relevant legislation including 2001/20/EC, performed from screening onwards.

All SAEs (initial and follow-up information) will be reported electronically through [REDACTED] Remote Data Capture (RDC) platform within 24 hours of the discovery of the event or information. Manual SAE report forms are available in the Study Instructions Manual, however manual SAE report forms may be faxed to [REDACTED] PVG only in the event RDC is not functioning, and must be entered into RDC when it becomes available. The Sponsor may request follow-up and other additional information from the Investigator (e.g., hospital admission/discharge notes and laboratory results).

All deaths should be reported with the primary cause of death as the AE term, as death is typically the outcome of the event, not the event itself. The primary cause of death on the autopsy report should be the term reported. Autopsy and postmortem reports must be forwarded to the Sponsor's Medical Monitor, or designee, as outlined above.

If study drug is discontinued because of an SAE, this information must be included in the SAE report.

Investigators must report SAEs to their governing IRBs/ECs in writing as soon as possible and in accordance with national and local laws and regulations.

8.15 Treatment and Follow-up of Adverse Events or Serious Adverse Events

From the time the subject signs informed consent until 28 days after the last vaccination, all untoward medical events (as defined in [Section 8.2](#) and exceptions as noted in [Section 8.4](#)) will be documented as (S)AEs through the Treatment phase of the study or through the last visit of the Treatment phase of the study for subjects who withdraw early.

All (S)AEs assessed as not related to study vaccine will be followed as clinically indicated until resolved, stabilized, or if non-resolving, until 28 days after the last vaccination, whichever comes first. If a clear explanation is established, it should be recorded on the CRF.

If an SAE is assessed as possibly or definitely related to study vaccine, it must be followed until either the event has resolved, stabilized, or is deemed to be non-resolvable by the investigator.

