1.5 Safety of Poxviral Vectors

1.5.1 Vaccinia Virus

Vaccinia virus causes a transient infection, with elimination of viral components over several weeks. Host cells infected with vaccinia virus are short lived (days) and die by a mixed form of apoptosis/necrosis. Vaccinia replicates in the cytoplasm of infected cells, and viral DNA does not integrate into the host cell DNA. Vaccinia virus is known to be shed from the wound site in traditional dermal scarification based vaccination.

The use of vaccinia virus for worldwide eradication of smallpox provides a safety database with number of observations in the millions. Geographical differences in strains of vaccinia virus used as well as differences in reporting practices, diagnostic and follow-up criteria between countries are a cause of some discrepancies in the incidences of adverse events reported, but the overall picture of vaccinia virus safety is very well known. An additional set of data is provided by recent vaccination campaign of military and civilian vaccinations in the US.

A number of events post vaccination are expected and considered to be normal: fever, myalgia, headache, fatigue, chills, nausea, soreness and erythema at the vaccination site, local lymphadenopathy. Satellite lesions around the vaccination site have been reported as well as local edema. These symptoms are self-limiting, last for around three weeks after vaccination and rarely are a cause for serious concern (Frey 2002, Fulginiti 2003). Mild adverse reactions that can occur post vaccination are bacterial superinfection of vaccination site, erythema multiforme (EM) and generalized vaccinia. Superinfection is a rare event with incidence from 0.14 to 55 cases per million according to different reports (Vellozzi 2004). EM most often presents as papules, plaques or urticaria which may be symmetrical, may involve palms and soles. EM resolves spontaneously and requires no special care. A development of Stevens-Johnson syndrome with mucosal involvement is extremely rare, with only one case noted in the 2003-2004 vaccination campaign in the US (<1 per 1,000,000) (Fulginiti 2003, Neff 2008).

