7.4 End-of-Treatment Visit – Week 25 or When A Subject Discontinues Treatment

The End-of-Treatment visit is approximately 4 weeks \pm 3 days after the last injection of vaccine or placebo. The tests and evaluations listed for the End-of-Treatment/Early Termination Visit should be carried out at the time of any premature subject withdrawal (subject- or investigator-directed) or whenever the investigator feels that the subject will be or is unable or unwilling to make any further visits. If a subject discontinues treatment early for any reason, every attempt should be made to document the reason for the discontinuation.

Any subject who requests to stop study treatment or has been withdrawn from study treatment before completion of the protocol-specified treatment duration will be strongly encouraged to complete the evaluations below, and encouraged to participate in the Long-Term Follow-Up Phase of the study provided the subject has not withdrawn full consent.

1. Adverse events – will be collected by non-directive questioning, self-reported or directly observed occurring since last visit, and discuss and/or resolve any previously reported or ongoing events.
2. Concomitant medications – record all medications being taken currently and record all previously taken, but discontinued drugs.
3. QoL (FACT-P, BPI-SF and EQ-5D-3L) where translations are available
4. Complete PE including VS, sitting BP, heart rate, RR, temperature, and weight
5. ECOG performance status
6. Blood samples will be obtained for:
 - a. Hematology (CBC and differential, RBC with indices, platelet count)
 - b. Serum chemistry (BUN, creatinine, ALT, AST, alkaline phosphatase, total bilirubin, LDH, sodium, potassium, chloride, bicarbonate, calcium and glucose)
 - c. Coagulation panel (PT/(INR) / PTT)
 - d. C-reactive protein

- e. Serum PSA and PAP
 - f. Serum for immune and biomarker status
 - g. Peripheral blood RNA/biomarker analysis
 - h. CTC quantification (US sites only)
 - i. Immune functional assays (US sites only)
- 7. Urinalysis
 - 8. 12-lead ECG
 - 9. Bone scan
 - 10. CT scan with contrast* (abdomen and pelvis)

* For subjects with allergies to contrast agents, MRIs for abdomen and pelvis may be performed. Only in cases where MRI is unavailable may a non-contrast CT be performed. For subjects enrolled in Germany, MRI must be used as the primary imaging modality.

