7.5 Assessments During Long-Term Follow-Up

The Long-Term Follow-Up (LTFU) phase begins immediately after the End-of-Treatment visit regardless of the total number of vaccinations actually received by a subject. The first visit is 6 calendar months \pm 14 days after the End-of-Treatment visit with consecutive visits every 6 months \pm 14 days thereafter. Subjects who progress prior to or during the LTFU phase will continue to be followed for survival and as described below until study closure or death.

First LTFU visit at 6 Months \pm 14 Days from the End-of-Treatment visit

- 1. Concomitant medications (limited to the treatment of prostate cancer therapy). All previously recorded medication entries should be reviewed for stop dates.
- 2. Prostate cancer treatment update for procedures, including interim unscheduled laboratory tests and/or radiological assessments.
- 3. Update for newly diagnosed autoimmune disease.
- 4. Physical exam (limited to assessment of subject's prostate cancer status including prostate cancer progression), vital signs, and weight.
- 5. QoL (FACT-P, BPI-SF and EQ-5D-3L)
- 6. Blood samples obtained for:
 - i. Serum for immune and biomarker status.
 - ii. Peripheral blood RNA/biomarker analysis
 - iii. CTC quantification (US sites only)
 - iv. PSA and PAP

v. Immune functional assays (US sites only)

7. CT* and bone scan

* For subjects with allergies to contrast agents, MRIs for abdomen and pelvis may be performed. Only in cases where MRI is unavailable may a non-contrast CT be performed. For subjects enrolled in [REDACTED], MRI must be used as the primary imaging modality.

Subsequent LTFU visits thereafter (every 6 Months ± 14 Days, phone call is acceptable)

1. Survival status
2. Any anti-prostate cancer therapy
3. Update for newly diagnosed autoimmune disease

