8.4 Collecting and Recording Adverse Events

The Investigator will monitor the occurrence of adverse event for each subject during the course of the study. All AEs (as defined above) reported by the subject, observed by the Investigator, or documented in medical records will be listed on the AE CRF, whether believed by the Investigator to be related or unrelated to the study vaccine.

All AEs must be reviewed, graded and causality determined by an Investigator listed on the form FDA 1572 at the research center reporting the event(s). Collection of adverse events begins at the time the subject signs informed consent and continues for 28 days following administration of the last dose of study medication.

Adverse event terms should be recorded concisely, using acceptable medical terms. When possible, a diagnosis (*i.e.*, disease or syndrome) rather than the component signs and symptoms should be recorded on the CRF (*e.g.*, congestive heart failure rather than dyspnea, rales, and cyanosis). However, signs and symptoms considered unrelated to syndromes or diseases are to be recorded as individual adverse events on the CRF (*e.g.*, if congestive heart failure and severe headache are observed at the same time, each event is to be recorded as an individual adverse event). Only abnormal laboratory values that result in clinical sequelae or require medication for treatment should be recorded as an adverse event. The adverse event should not be recorded as a procedure or clinical measurement (*i.e.*, a laboratory or vital sign). The underlying reason for the procedure or the abnormal clinical measurements, and, whenever possible, a diagnosis, should be recorded. The diagnosis should be recorded; not the individual lab test name.

Death is considered to be an outcome of an adverse event. The cause of death should be recorded on the AE CRF (*e.g.*, congestive heart failure with an outcome of death rather than the term "death").

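### The protocol conflicts with itself on when adverse-event collection ends for men who stop vaccination early, so active ascertainment can stop before day 28

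*Protocol*

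**What the plan says.** Protocol 8.4 starts AE collection at consent and says that it "continues for 28 days following administration of the last dose of study medication". Section 8.12, which defines the reporting period, says that it "ends 28 days following administration of the last dose of study medication". Neither makes an exception for early stoppers. Section 8.13 sets the same limit for serious events (SAEs): "Any SAE that occurs after the subject signs informed consent and until 28 days following administration of the last dose of study medication".

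Section 8.15 counts from a different point, 28 days after the last vaccination. The same sentence then ties documentation to the Treatment phase, or "through the last visit of the Treatment phase of the study for subjects who withdraw early".

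Under 8.7, men with intolerable toxicity "will be immediately rolled over onto the Long-Term Follow-Up (LTFU) phase of the study". The sentence goes on to say that they are followed for safety and vital status, and 6.7 and 5.4.1 also keep men who stop vaccination in safety follow-up.

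Section 7.4 gives the last treatment visit two timings. It falls about four weeks (± 3 days) after the last injection, but its evaluations "should be carried out at the time of any premature subject withdrawal (subject- or investigator-directed"). Under 7.5, the long-term follow-up (LTFU) "phase begins immediately after the End-of-Treatment visit regardless of the total number of vaccinations actually received by a subject". The first LTFU visit is six months ± 14 days later. Its list has no AE item other than newly diagnosed autoimmune disease, and the adverse-event row of the Schedule of Events (14.1) stops at Week 25.

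SAP 9.1 tabulates treatment-emergent events with onset before last dose plus 28 days. SAP Section 4 makes the number of subjects in the arm the default denominator.

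**The concern.** For a man who completes treatment, the Week 25 visit and the end of the 28-day window nearly coincide, so one visit serves both. For a man who stops early they can come apart. The visit may be held when he stops, he then passes into LTFU, and no later scheduled contact asks about AEs within the window.

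Toxicity is one reason for stopping, so the shorter observation can depend on the outcome being measured. It could also differ by arm: only the two vaccine arms receive replicating vaccinia, and only in Week 1. For smallpox vaccination, Protocol 1.5.1 says of the expected reactions: "These symptoms are self-limiting, last for around three weeks after vaccination". That period fits inside 28 days but would outlast a visit held in the first two weeks. With crude percentages over all subjects in the arm, days on which nobody asked count as days without an event.

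**Working it through.** The documents state no figure to reproduce. The check compares the passages and applies the protocol's own visit weeks.

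**Step 1. The end of collection, section by section**

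| Section | End of AE collection | Exception for early stoppers |
|---|---|---|
| 8.4, 8.12 | last study medication + 28 days | none |
| 8.13 (SAEs only) | last study medication + 28 days | none |
| 8.15, opening | last vaccination + 28 days | none |
| 8.15, closing | last Treatment-phase visit | those who withdraw early |
| 7.5 and 14.1 | no AE item after End-of-Treatment (autoimmune disease only) | not applicable |

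**Step 2. Two clocks.** Let V be the day of the last vaccination. GM-CSF or its placebo is given on that day and the next three (14.1, note 2), so the last study medication falls on V + 3 if all four doses are taken.

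- Vaccination clock (8.15): the window ends on V + 28.
- Study-medication clock (8.4, 8.12): it ends on V + 3 + 28 = V + 31.

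**Step 3. Uncovered days.** Let g be the number of days from the last vaccination to the last visit at which AEs are asked about. Uncovered days are max(0, 28 − g) on the vaccination clock and max(0, 31 − g) on the study-medication clock. Vaccinations fall in Weeks 1, 3, 5, 9, 13, 17 and 21. Ranges apply the ± 3-day window to the last visit only.

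| Case | g | Vaccination clock | Study-medication clock |
|---|---|---|---|
| Stop after Week 1 or 3; seen at next scheduled visit | 14 (11–17) | 14 (11–17) | 17 (14–20) |
| Stop after Week 5, 9, 13 or 17; seen at next scheduled visit | 28 (25–31) | 0 (0–3) | 3 (0–6) |
| Stop after Week 1; seen on Day 5 after all four GM-CSF/placebo doses | 4 | 24 | 27 |
| Visit held four weeks after last injection (7.4) | 28 (25–31) | 0 (0–3) | 3 (0–6) |
| Completer, Week 21 to Week 25 | 28 (25–31) | 0 (0–3) | 3 (0–6) |

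Using the next scheduled visit is an assumption; 7.4 does not say it. In the Day 5 case the man was vaccinated on Day 1. The windows end on Day 29 and Day 32, leaving Days 6–29 (24 days) and Days 6–32 (27 days). The completer row shows that the residual of about three days comes from the difference between the clocks, not from early stopping.

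**Step 4. Next contact.** Six months is about 6 × 30.44 = 183 days. With ± 14 days, the first LTFU visit comes 169–197 days after the termination visit, long after either window has closed.

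**Step 5. Number of men.** The documents give no early-stopping rate and no distribution of termination-visit timing, so no count follows.

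**The case against.** The strongest reply is that 28 days is the rule and 8.15 contains one badly drafted clause. That sentence itself opens with 28 days, its next paragraph follows unrelated events up to the same limit, and 8.12 is the section that defines the reporting period. Section 8.7 promises safety follow-up after rollover. Withdrawing early may mean leaving the study, where ending at the last visit is unremarkable. Section 8.4 records AEs that subjects report or that appear in medical records, so collection does not depend wholly on a visit.

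Much of this stands. A reader might infer that 8.15 and 8.7 plainly end collection at the last visit for every man who stops vaccination. The documents do not support that; they conflict. But the reply does not close the gap. Section 7.4 also uses withdrawal for leaving study treatment, and the safety follow-up promised in 8.7 has no AE assessment behind it in 7.5 or 14.1.

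A reader might also infer that SAE incidence is biased downward. That is largely answered: 8.12 and 8.13 keep the 28-day duty for SAEs, 8.12 still takes related SAEs that come to light after the study, and 6.8 and 8.4.3 require notification of suspected serious vaccinia reactions within 24 hours of awareness.

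The vaccinia argument is limited too. It concerns only the earliest stoppers. The three-week figure comes from conventional smallpox vaccination, and 1.5.1 expects milder injection-site reactions with subcutaneous dosing. Section 1.3 calls the placebo and vaccinia site reactions generally indistinguishable, which weakens any expected difference between arms.

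**Conclusion.** The inconsistency is real and should be corrected. Following 8.15, 7.4, 8.7 and 7.5 as written can leave part of the 28-day window in 8.4 and 8.12 without any scheduled AE contact.

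The size depends on when the termination visit is held, and 7.4 gives two answers. At the next scheduled visit (assumption), stops after Week 1 or Week 3 leave roughly half the window uncovered; later stops leave little or nothing beyond what completers also lose. A visit just after dosing leaves nearly all of it uncovered, and a visit four weeks after the last injection almost none. The Day 5 case is a near-worst illustration, not a typical loss. Applying an assumed stopping rate to the 1,200 men would not give the number affected, because it would include men who lose nothing.

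The SAP does not claim that every man was observed for 28 days. That its tables treat unobserved days as event-free is an inference from its cut-off and denominator. Any resulting bias in event incidence is possible, of unknown size, and mainly a matter of non-serious events.

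**What to change.** - **Protocol 8.15:** delete the clause "through the last visit of the Treatment phase of the study for subjects who withdraw early" with the word that joins it to the sentence. State the 8.12 window for every subject, whatever the reason for stopping. Count from the last dose of study medication in both places where 8.15 now counts from vaccination.
- **Protocol 8.7:** state that rollover to LTFU ends treatment but does not end AE or SAE collection before the window closes.
- **Protocol 7.4, 7.5 and 14.1:** where the termination visit falls before the end of the window, add one AE telephone contact at its end, unless full consent has been withdrawn.
- **SAP 9.1:** keep the cut-off, and add a sentence on how men observed for less than the full window are handled.

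The cost is protocol wording, one SAP sentence and one call per affected early stopper. Slightly more AEs may be recorded. Nothing changes in dosing or in the survival analysis.
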